16.1.4 Phase 1 Dose Escalation

16.1.5 **Objectives**

16.1.5.1 **Primary Objective**

The primary objective of this Phase 1 study is to determine the maximum tolerated dose safety and toxicity profile of BMX-001 administered in conjunction with standard radiotherapy and cisplatin among patients with newly diagnosed head and neck cancer. Two dose levels were completed: 1) 7 mg/subject and 2) 14 mg/subject followed by maintenance doses given twice weekly of 1) 3.5 mg/subject and 2) 7 mg/subject. The toxicity profile will be done using the CTCAE version 4.03.

16.1.5.2 MTD

The MTD has been selected for studying in Phase 2 based on completed Phase 1 human trials of BMX-001.

16.1.5.3 Secondary Objectives of Phase 1 Study

Adverse events will be tabulated in a different manner for the manuscript summarizing the results of this study, annual reports for the Safety Oversight Committee, and the final report included within ClinicalTrials.gov.

For the manuscript, adverse events that are possibly, probably, and definitely treatment-related will be summarized. For each type of toxicity, the maximum grade experienced by each patient will be summarized with frequency distributions within each treatment group.

For ClinicalTrials.gov, serious adverse events and other adverse events will be summarized separately. These tabulations will reflect the number of patients who experience each type of toxicity regardless of grade or attribution.

CTCAE data will be collected and compared:

- To assess the effect of BMX-001 in combination with RT and concurrent cisplatin in newly diagnosed HNSCC patients on overall survival (OS), progression free survival (PFS), and initial response to treatment.
 - Kaplan-Meier methods will be used to graphically describe the distribution of overall survival (OS) and progression-free survival. OS is defined as the time interval between initiation of protocol treatment and death, with overall survival censored at last follow-up if the patient remained alive. PFS is defined as the time between initiation of protocol treatment and disease progression or death. If the patient remains alive without disease progression, then PFS will be censored at last follow-up. Median OS and PFS, as well as 6- and 12-month estimates of OS and PFS, will be estimated from the Kaplan-Meier curve.
- To examine the impact on mucositis of BMX-001 in combination with RT and concurrent cisplatin in treatment of newly diagnosed patients with locally advanced head and neck cancers by evaluating the degree of oral mucositis at 30-39 Gy, 40-49 Gy, 50-59 Gy, and 60-70 Gy, the duration of oral mucositis, and evaluation of mucositis-related patient-reported outcomes.
 - The duration of mucositis at 30-39 Gy, 40-49 Gy, 50-59 Gy, and 60-70 Gy, will be descriptively summarized using means and 95% confidence intervals (CIs). The evaluation of mucositis-related patient-reported outcomes at 30-39 Gy, 40-49 Gy, 50-59 Gy, and 60-70 Gy, will be descriptively summarized using frequencies, percentages, and 95% CIs.
- 3. To examine the impact on xerostomia of BMX-001 in combination with RT and concurrent cisplatin by evaluating degree of xerostomia at 30-39 Gy, 40-49 Gy, 50-59 Gy, and 60-70 Gy, the duration of xerostomia, and evaluation of xerostomia-related patient-reported outcomes.
 - The duration of xerostomia at 30-39 Gy, 40-49 Gy, 50-59 Gy, and 60-70 Gy, will be descriptively summarized using means and 95% confidence intervals (CIs). The

evaluation of xerostomia-related patient-reported outcomes at 30-39 Gy, 40-49 Gy, 50-59 Gy, and 60-70 Gy, will be descriptively summarized using frequencies, percentages, and 95% Cls.

4. To examine the impact on radiation dermatitis of BMX-001 in combination with RT and concurrent cisplatin by evaluating degree of radiation dermatitis at 30-39 Gy, 40-49 Gy, 50-59 Gy, and 60-70 Gy, the duration of radiation dermatitis, and evaluation of radiation dermatitis-related patient-reported outcomes.

The duration of radiation dermatitis at 30-39 Gy, 40-49 Gy, 50-59 Gy, and 60-70 Gy, will be descriptively summarized using means and 95% confidence intervals (CIs). The evaluation of radiation dermatitis-related patient-reported outcomes at 30-39 Gy, 40-49 Gy, 50-59 Gy, and 60-70 Gy, will be descriptively summarized using frequencies, percentages, and 95% CIs.

5. To characterize the single-dose and repeated-dose pharmacokinetic profiles of BMX-001 when delivered in combination RT and concurrent cisplatin.

16.1.5.4 **Exploratory Objectives for Phase 1 Study**

The mean change between baseline and each follow-up assessment for HRQoL will be descriptively summarized using means and 95% CIs.

16.2 Phase 2

16.2.1 **Primary Endpoint**

1) The primary endpoint is incidence of severe oral mucositis (grade 3 and 4).

The incidence rates of severe oral mucositis graded by CTCAE as grade 3 or 4 will be descriptively summarized and calculated.

- 2) The secondary endpoints are:
 - 1. Median duration (days) of severe oral mucositis
 - 2. Median time (days) to onset of severe oral mucositis
 - 3. Incidence of grade >/= 2 Xerostomia at month 1 and 6 post completion of RT.

16.2.2 Objectives/Endpoint and Data Analyses

16.2.2.1 **Primary Objectives for Phase 2**

 To confirm the safety and tolerability of the MTD of BMX-001 in conjunction with RT and concurrent cisplatin in cohort of HNSCC patients.

The incidence rates of adverse events (AE) will be described without regard to causality. AE incidence occurring within each cycle will be described. The frequency of overall toxicity, categorized by toxicity grades, will also be summarized. Listings of laboratory results collected at baseline and during the study will be generated and descriptive statistics summarizing changes in laboratory tests over time will be presented.

Adverse events will be tabulated in a different manner for the manuscript summarizing the results of this study, annual reports for the Safety Oversight Committee, and the final report included within ClinicalTrials.gov

For the manuscript, adverse events that are possibly, probably, and definitely treatment-related will be summarized. For each type of toxicity, the maximum grade experienced by each patient will be summarized with frequency distributions within each treatment group.

For ClinicalTrials.gov, serious adverse events and other adverse events will be summarized separately. These tabulations will reflect the number of patients who experience each type of toxicity regardless of grade or attribution.

2. To further explore efficacy based on the impact of BMX-001 on mucositis, xerostomia, and radiation dermatitis in treatment of newly diagnosed patients with locally advanced head and neck cancers by evaluating the degree of these adverse events at 30-39 Gy, 40-49 Gy, 50-59 Gy, and 60-70 Gy, the duration of the adverse events, and evaluation of related patient-reported outcomes. Comparison against historical controls will be made.

The duration of mucositis, xerostomia and radiation dermatitis, separately, at 30-39 Gy, 40-49 Gy, 50-59 Gy, and 60-70 Gy, will be descriptively summarized using means and 95% confidence intervals (CIs). The evaluation of mucositis, xerostomia, and radiation dermatitis, separately, at related patient-reported outcomes at 30-39 Gy, 40-49 Gy, 50-59 Gy, and 60-70 Gy, will be descriptively summarized using frequencies, percentages, and 95% CIs.

16.2.2.2 **Secondary Objectives for Phase 2**

1. To assess the efficacy based upon overall survival (OS), median progression free survival (PFS), and initial response to treatment

Kaplan-Meier methods will be used to graphically describe the distribution of overall survival (OS) and progression-free survival. OS is defined as the time interval between initiation of protocol treatment and death, with overall survival censored at last follow-up if the patient remained alive. PFS is defined as the time between initiation of protocol treatment and disease progression or death. If the patient remains alive without disease progression, then PFS will be censored at last follow-up. Median OS and PFS, as well as 6- and 12-month estimates of OS and PFS will be estimated from the Kaplan-Meier curve.

2. To assess radiographic response in locally advanced HNSCC patients treated with standard RT and cisplatin with BMX-001 at MTD.

The radiographic response (CR or PR) will be assessed as defined in 12.6.2. The radiographic response rate will be tabulated and reported using frequencies and 95% confidence intervals.

16.2.2.3 **Exploratory Objectives for Phase 2**

1. To further describe patient-reported outcomes of HRQoL in locally advanced HNSCC with standard RT, cisplatin, and BMX-001 at the MTD.

16.2.3 Interim Analysis for Phase 2

No interim efficacy analyses are planned given the length of time to assess an individual patient's outcome and the expected rapidity of patient accrual.

16.2.4 Sample Size Calculation for Phase 2

In this study, patients will receive BMX-001 at the Recommended Phase 2 Dose (RP2D). The ultimate goal of this study is to determine whether BMX-001 in combination with standard RT and cisplatin treatment is worthy of further investigation. The cohort will be compared with historical controls, which will be assessed for quality.

We will focus on the occurrence and severity of mucositis, xerostomia, and radiation dermatitis in this power calculation given that the study is not a randomized study, even though we are interested in comparing groups with respect to change in mucositis and xerostomia between protocol timepoints.

We anticipate accruing 48 patients which, for statistical purposes, we assume that approximately 40 will have available measurements of mucositis, xerostomia, and radiation dermatitis. We use a conservative estimate of a proportion of 0.50 since it results in the widest CI. A sample size of 40 produces a two-sided 95% exact confidence interval (Clopper-Pearson) with a width equal to 0.324 when the sample proportion is 0.50.

17 References

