4.1.2 Radiation-induced Damage

Radiotherapy for the treatment of head and neck cancers can produce severe therapy-induced side effects. Acute effects commonly appear within a week of starting radiotherapy and most people suffer from at least one of these unwanted side effects. The acute side effects can include: xerostomia, mucosal degradation (mucositis) and ulceration, edema, loss of taste (dysgeusia), difficulty swallowing and talking, ear aches, infections, hair loss, and radiation dermatitis. These acute problems can become so severe that radiation therapy has to be delayed, which can lead to reduced local control or at times, terminated. Long-term complications from radiation therapy directed to the head and neck region can include trismus (restriction on opening of the jaw), osteoradionecrosis, or breakdown of the mandible, loss of sensation, loss of taste, increased risk of dental caries (cavities), and decreased salivary function. Thus, quality of life can be severely compromised following the treatment of head and neck cancers. More concerning is the increase in non-cancer-related deaths in patients treated with concurrent high dose cisplatin and radiation in RTOG 91-11 as a result of long-term complications. This damage can occur anytime during radiation therapy and has been reported years after treatment. The long-term toxicities are a function of high dose radiation and volume of irradiated tissue, amplified by the addition of radio-sensitizing chemotherapy. Once the damage of normal tissue begins, it is usually progressive and irreversible. Because there is a 50-85% five year survival rate for patients treated for head and neck cancers, due in part to a rapidly increasing segment of younger patients experiencing HNSCC related to human papillomavirus infection, there are many people who are living with these long-term side effects (American Cancer Society, 2013 Statistics). Thus, the development of an effective radio-protector would improve the quality of life of many head and neck cancer patients.

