9.7.1 Radiation Therapy / Adverse Events

Grade 3-4 (CTCAE, v. 4.03) therapy-induced mucositis and/or dysphagia, which are enhanced by cisplatin, are expected to develop in about two thirds of patients. Nutritional evaluation prior to the initiation of therapy for a prophylactic gastrostomy (PEG) tube placement is highly recommended. Placement of a feeding tube should be recorded, as should use of a feeding tube during and after treatment (e.g., greater than or less than 50% of nutrition by tube). Other common radiation adverse events include: fatigue, weight loss, regional alopecia, xerostomia, hoarseness, transient ear discomfort, dysgeusia, headaches, loss of appetite, and skin erythema and desquamation within the treatment fields.

Less common long-term treatment adverse events include: hypothyroidism, loss of hearing, chronic swallowing dysfunction requiring permanent feeding tube, and cervical fibrosis. Much less common radiation adverse events include: tissue necrosis, secondary cancer, mandibular osteoradionecrosis (< 5% incidence with attention to the standard dental recommendations), and cervical myelopathy (< 1% with restriction of spinal cord dose to \le 45 Gy).

Summary of possible side effects of radiation therapy to the head and neck:

COMMON, SOME MAY BE SERIOUS

In 100 people receiving radiation therapy, more than 20 and up to 100 may have:

- Sores in the mouth and/or throat which can be painful and make it very difficult to chew and or swallow foods
- Mouth dryness or changes in taste and/or smell that may be permanent
- Thick saliva
- Hoarseness
- Tanning or redness and/or irritation of the skin in the head and neck area being treated with radiation
- Ear pain and/or pressure
- Fatigue
- Weight loss
- Permanent hair loss in the area treated with radiation (face, chin, neck)
- Loss of teeth or cavities in the teeth if strict dental care is not followed and/or hypersensitivity of teeth

OCCASIONAL, SOME MAY BE SERIOUS

In 100 people receiving radiation therapy, from 4 to 20 may have:

- Decrease in function of the thyroid gland that may require you to take thyroid replacement medicine to prevent you from feeling tired or sleepy
- Serious damage to the jawbone, voice box, skin, or other parts of the head and neck that may require a major operation to correct and, rarely, can even be life threatening
- Temporary pain or scarring around nerves in the shoulder that could cause numbness and/or weakness
- Breathing problems

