DLQI											
Questionnaires											
FACT-HN		X								X	X
Questionnaire,											
PRO-CTCAE HN											
Assessment of	X										X
measurable											
disease by											
imaging ^f											
Toxicity	X	Ongoing						X			
Assessment											
BMX-001g, h		X	X	X	X	X	X	X	X	X	
Cisplatin i			X	X	X	X	X	X	Xi		
Radiation		Daily Monday-Friday for 6-7 weeks ^k									

^a Screening evaluation should be done within 21 days of starting BMX-001. The screening evaluation and baseline evaluation may be combined. Informed consent may be done within 28 days of starting BMX-001.

b Study assessments for History and Physical, medications, weight, vital signs, CBC w/ diff, CMP, and mucositis will be obtained at screening, baseline, weekly during therapy, and following therapy at clinic visits in which timing is scheduled under standard of care. Screening CBC with diff and CMP prior to the first dose of Cisplatin need not be repeated on week one for chemotherapy naïve subjects per institutional practice. Study visits following therapy (Week 9 and forward) will be under SOC and at minimum will include study data collection for the CRF at a post-therapy visit within 1 month of completion of

radiation (or within 1 month of completion of BMX-001 treatment) and at 6 and 12 months post radiation \pm 1 month. Mucositis will be scored using the CTCAE version 4.03. Toxicity assessment will continue to be obtained during year 1 to identify late toxicities possibly related to SOC or with study drug. PT/aPTT will be measured once and can be done at either screening or baseline.

- ^c Blood pressure and heart rate will be measured pre-dose and then after 30 (\pm 5), 60 (\pm 5), 120 (\pm 10) minutes on the loading dose. It will be checked pre-dose, and post-dose at 30 (\pm 5), and 60 (\pm 5) minutes all other days of BMX-001 administration.
- ^d Phase 2: ECG will be done at screening and will also be done pre-dose as well as at 60 (± 15) minutes after dosing on the loading day and on a maintenance dose injection day during week 1 and week 4, both pre and post dose at 60 (± 15) minutes.
- e Saliva production will be measured on baseline and the post-therapy measurement will be obtained at clinic visit within 1 month of the end of radiation therapy and at 6 and 12 months ± 1 month. If the post-therapy measurement cannot be obtained, this will not be considered a protocol deviation.

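### Toxicity durations are to be reported as simple means with no rule for unresolved cases or for dating resolution between widely spaced visits, so the xerostomia figure depends on an unstated choice

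*Combined protocol and SAP*

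**What the plan says.** Phase 2 objective 2 (Sections 5.3 and 16.2.2.1) covers the degree and duration of mucositis, xerostomia and radiation dermatitis, and the related patient-reported outcomes. Durations, by toxicity and dose band, "will be descriptively summarized using means and 95% confidence intervals (CIs". The section adds: "Comparison against historical controls will be made". No reference duration is given.

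The plan does not say how an unresolved toxicity enters the mean, or on what date a toxicity ends if it is present at one visit and gone at the next. For survival outcomes, Section 16.2.2.2 uses Kaplan-Meier and states a rule: "If the patient remains alive without disease progression, then PFS will be censored at last follow-up".

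Four other places bear on the point:
- **Persistence.** Section 9.7.1 lists among common radiation effects "Mouth dryness or changes in taste and/or smell that may be permanent". Section 4.1.2 says of normal-tissue damage: "Once the damage of normal tissue begins, it is usually progressive and irreversible".
- **Visits.** Footnote b to the Section 13 schedule has assessments "following therapy at clinic visits in which timing is scheduled under standard of care". The required minimum is a visit within 1 month of completing "radiation (or within 1 month of completion of BMX-001 treatment) and at 6 and 12 months post radiation", with a window of 1 month either way.
- **Length of follow-up.** The same footnote collects toxicity during year 1, Section 13.3 gives about 24 months, and Section 13.4.2 gives six months after withdrawal for toxicity or progression.
- **Frequency on treatment.** Mucositis is scored weekly during therapy (Section 13.1.5).

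**The concern.** The duration of a toxicity is a time-to-event quantity. It is right-censored if the toxicity is still present at the last assessment. If it has resolved, its end is known only to lie between two visits. A simple mean needs one number per patient, so someone must decide whether unresolved patients are left out or given a cut-off value, and where in the gap resolution is placed. The plan leaves both choices open for durations, although it settles the matching question for OS and PFS.

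At stake is the meaning of a named component of objective 2. A radioprotector might lower the share of patients left with lasting dry mouth, and the reported mean should respond to that. A comparison with historical controls cannot be interpreted unless both sides use the same rule.

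**Working it through.** **The plan's own figure.** No design figure is given for durations. The only one is the width of the exact 95% interval in Section 16.2.4. For 20 of 40 the Clopper-Pearson limits are 0.338 and 0.662, a width of 0.324. It reproduces and does not depend on this point.

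**Inputs.** Visits at 1, 6 and 12 months after RT come from footnote b. The documents give no resolution rates, so these are assumptions: onset on day 28, RT ending on day 47, a share p with permanent xerostomia, and exponential recovery in the rest with median 180 days from onset. Resolution before the 1-month visit is recorded at that visit, with the end of RT as the previous assessment.

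**Step 1: visit times from onset.** RT ends at 47 − 28 = 19 days. With a month of 30.44 days, the visits fall at 49.4, 201.6 and 384.25 days.

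**Step 2: recoverers found clear at each visit.** F(t) = 1 − 0.5^(t/180) gives 0.1734, 0.5400 and 0.7723. The shares newly clear are 0.1734, 0.3666 and 0.2323.

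**Step 3: unresolved at 12 months.** U = p + (1 − p)(1 − 0.7723).
- p = 0.2: 0.2 + 0.8 × 0.2277 = 0.382
- p = 0.5: 0.5 + 0.5 × 0.2277 = 0.614

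**Step 4: sums over resolved recoverers.**
- Dated at the first clear visit: 0.1734 × 49.4 + 0.3666 × 201.6 + 0.2323 × 384.25 ≈ 171.8
- Dated at the interval midpoint (34.2, 125.5, 292.9 days): ≈ 120.0

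**Step 5: the mean under each rule.** With unresolved cases dropped, the mean is the sum divided by 0.7723, and p cancels. With them counted to the 12-month visit, it is (1 − p) × sum + U × 384.25. The true mean restricted to that visit is 384.25p + (1 − p) × (180/ln 2) × 0.7723.

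| Mean duration (days) | p = 0.2 | p = 0.5 | Change |
|---|---|---|---|
| Dropped, midpoint | 155 | 155 | 0 |
| Dropped, first clear visit | 222 | 222 | 0 |
| Counted to 12 months, midpoint | 243 | 296 | 53 |
| Counted to 12 months, first clear visit | 284 | 322 | 38 |
| True mean restricted to the 12-month visit | 237 | 292 | 55 |
| True mean restricted to 24 months after RT | 346 | 497 | 151 |

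The last row uses the same formula with a limit of 19 + 730.5 = 749.5 days. At p = 0.2 the rule alone moves the mean by 284 − 155 = 129 days.

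**Step 6: other assumptions for xerostomia.** With 20% to 60% permanent and recovery averaging 4 months after RT in the rest, simulation gives 24% to 62% unresolved at 12 months. For 50% against 30% permanent, with resolution dated at the first clear visit, cases counted to 12 months give 9.11 and 7.96 months after RT. That is a difference of 1.15, against a true 12-month restricted difference of 1.64. With unresolved cases dropped, both means are 5.92.

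**Step 7: mucositis and dermatitis.** Assume that all cases resolve, on average 0.5 to 2 months after RT (Weibull, shape 1.5), after one month of toxicity during RT, with extra visits at about 1 and 2 weeks. The true mean is 1.5 to 3.0 months. Dating at the first clear visit gives 2.1 to 5.7 (high), the midpoint 1.7 to 3.8 (high), and the last visit with the toxicity present 1.3 to 1.9 (low).

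**The case against.** A reader might infer three stronger things, and the documents support none of them.

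**That the means are biased low throughout.** Against the true mean restricted to the 12-month visit, counting unresolved cases to that visit and dating at the first clear visit is biased high (284 against 237 days). These rules understate only against a longer horizon. Dropping unresolved cases falls below 237 in both versions. For mucositis and dermatitis the sign depends on the dating rule.

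**That the mean cannot show a change in permanent injury.** That is true only if unresolved patients are dropped. The opening of Section 16 expects all treated patients in all analyses, which points the other way. With midpoint dating and a 12-month horizon, the mean moves by 53 days against a true 55, so a stated rule nearly repairs it. But including every patient does not say what duration an unresolved patient receives.

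**That many cases of all three toxicities will be unresolved.** Only mouth dryness is said to be possibly permanent. Section 4.1.2 lists mucositis and dermatitis as acute effects, and its sentence on irreversibility follows a discussion of long-term complications. No unresolved proportion is given for any of the three.

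It is also fair to say that persistence is measured elsewhere: grade 2 or higher xerostomia at months 1 and 6, saliva production and XeQoLS to 12 months, and a median for the duration of severe mucositis. Standard-of-care visits may narrow the gaps. The objective is exploratory and the summary descriptive. All of this limits the consequence. It does not supply the rule: the xerostomia endpoint stops at month 6, a missed post-therapy saliva measurement is not a deviation, and no estimator is named for the mucositis median.

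**Conclusion.** The point holds as a gap with a better method readily available. For xerostomia, the planned mean is undefined until someone chooses how unresolved cases and end dates are handled. Under the assumed 20% permanent share and 180-day median, that choice alone moves it between about 155 and 284 days. Dropping unresolved cases hides a rise in the permanent share from 20% to 50%. Cutting off at 12 months shows it, attenuated to 38 of 55 days with first-clear-visit dating and nearly in full with midpoint dating, but well short of the 151-day change over 24 months.

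The sizes rest on assumed rates. The dependence on an unstated rule does not. For mucositis and dermatitis the bias may go either way. The primary endpoint, incidence of grade 3 or 4 mucositis, and the sample-size statement are unaffected.

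**What to change.** In Section 16.2.2.1:
- Replace the simple mean, at least for xerostomia, with a time-to-resolution estimate: Kaplan-Meier, or an interval-censored (Turnbull) estimate between the last visit with the toxicity and the first without it. Censor unresolved patients at their last assessment.
- Report a median, or a mean restricted to a stated horizon such as 12 months after RT. Reconcile the year-1 and 24-month follow-up statements so that the horizon is clear.
- Report the proportion still at grade 2 or higher at 1, 6 and 12 months with exact 95% intervals.
- If a simple mean is kept for mucositis and dermatitis, state the end-date rule.
- Apply the same rule and horizon to any historical comparison.

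The cost is SAP wording and slightly more analysis, using data already scheduled. One drawback is that the median may have to be reported as not reached, which is a reason to give the restricted mean and the proportions as well.
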